**Blood Sampling**: Blood samples will be drawn as part of this study. Arterial blood gas samples will only be obtained for patients with an indwelling arterial line. Placement of an Aline is not a requirement for the study, but likely standard of care (SOC) for this patient population. The blood samples will be collected the day prior to voxelotor administration, on study day 1 - 5, and on the 2 wash out days following voxelotor administration. Blood will be collected and sent to a core laboratory for measurement of erythropoetin levels (for evidence of renal medullary hypoxia), drug trough level measurement via pharmacokinetics (PK), and P50. Local lab will be used for Hematology and Chemistry. A total of 109 mls of blood will be collected for this study.

See Schedule of Activities Table 2.

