Physiological measures and laboratory data to be recorded from electronic medical record (EMR) are detailed on the Schedule of Activities Table 2.

Table 2: Schedule of Activities and/or other clinical outcomes

Table 2. Schedule of F	Bas	eline rements	Dosing Period				Wash out Period		
Study Day	D-2	D-1	D1	D2	D3	D4	D5	D6	D 7
Screening	X								
Consent	X								
Voxelotor Dosing			X	X	X	X	X		
Physiological									
ESLD and ALI cohort (At rest and with exercise*)									
$SpO_2$	X	X	X	X	X	X	X	X	X
FiO 2	X	X	X	X	X	X	X	X	X
S/F ratio calculation	X	X	X	X	X	X	X	X	X
HR	X	X	X	X	X	X	X	X	X
ALI cohort									
paO 2	X	X	X	X	X	X	X	X	X
SaO 2	X	X	X	X	X	X	X	X	X
P/F ratio calculation	X	X	X	X	X	X	X	X	X
paCO 2	X	X	X	X	X	X	X	X	X
A-a gradient calculation	X	X	X	X	X	X	X	X	X
Borg Dyspnea Scale rating	X	X	X	X	Х	X	Х	X	X
Laboratory									
Erythropoietin (5ml)		X		X				X	
PK (2ml)		X	X	X	X	X	X	X	X
P50 (3ml)		X	X	Х	X	X	X	X	X
BMP (4.5ml)			X	X	X	X	X	X	
CMP (4.5ml)		X							X
CBC (3ml)		X	X	X	X	X	X	X	X
Pregnancy test (2 ml)		X							
Con meds	X	X	X	X	X	X	X	X	X
Adverse Events			X	X	X	X	X	X	X

\*only if feasible, ambulatory patients only. Exercise protocol is SOC and data collected will be reviewed from medical record.

\*\*

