# 4 Subject Selection and Withdrawal

#### 4.1 Inclusion Criteria

- 1. Oxygen dependency due to an end-stage lung disease (pre-lung transplant population) or ALI/acute lung injury (for example but not limited to primary allograft dysfunction, infectious pneumonia, aspiration, non-cardiogenic pulmonary edema). ALI will be defined as per Berlin criteria with a P/F ratio < 100 denoting severe acute respiratory distress syndrome (ARDS), < 200 denoting moderate and < 300 mild ARDS. ALI and mild ARDS are considered synonymous. In the event of inability to obtain arterial blood gas analysis to calculate a P/F ratio, we will consider a range of patients requiring standard nasal cannulae flowing at 6 LPM (liters per minute) to maintain SaO2 > 90% as ALI, and Salter High -Flow nasal cannulae at 12-15 LPM in order to maintain SaO2 > 85% as severe ARDS.
- 2. At least 48 hours of stable, increased oxygen requirement or ventilatory support prior to the start of drug administration if consented.

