#### 7.2 Statistical Methods

Descriptive statistics for patient characteristics and baseline factors will be presented as median and interquartile range for continuous variables and number and percentage for categorical variables. The primary outcome will be change in S/F ratio from baseline to 2 days after initiation of voxelotor treatment, and the secondary outcome will be change in S/F ratio from baseline to 5 days after initiation of voxelotor treatment. Each will be compared using the Wilcoxon Signed Rank test. The baseline value will be defined as the median S/F ratio measurement during the 48-hour period before initiation of voxelotor treatment. Similarly, the

\*only if feasible/ ambulatory patients only. Exercise protocol is SOC and data collected will be reviewed from medical record.

day 2 and day 5 S/F ratio values will be defined as the median S/F ratio measurement on the second and fifth days after initiation of treatment.

All S/F ratio values will also be analyzed using a mixed-effects model with a random intercept for each patient and time in hours (relative to initiation of voxelotor treatment) as a fixed effect. Quadratic and cubic terms for time will also be included to allow for flexible modeling of treatment effect over time. We will tabulate and report all observed adverse events occurring during this trial.

For the ALI group with an arterial line in place, the PaO2/FiO2 (P/F) ratio will also be compared in a similar manner to identify whether any improvement in S/F ratio is due to clinical improvement of ALI, as reflected in the P/F ratio. The concept of Voxelotor use is an improvement in the S/F ratio (the result of left-shift in p50) for a given P/F ratio (the result of pulmonary function limiting PaO2). This may be especially important for the ALI sub-study cohort, as ALI could improve during the 5 day dosing period. Realistically, however, such progress is typically slow and, in contrast, the end-stage lung disease cohort would not be expected to improve and S/F ratio alone would reflect voxelotor effect without the need to track P/F ratios.

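### The P/F check on ALI recovery and the S/F analysis rest on different patients and days, so the two changes cannot be set against each other to separate recovery from drug effect

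*Combined protocol and SAP*

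**What the plan says.** Section 7.2 tests the change in S/F from baseline to Day 2 (primary) and Day 5 (secondary) with the Wilcoxon signed rank test, and adds a longitudinal analysis: "All S/F ratio values will also be analyzed using a mixed-effects model with a random intercept for each patient". Table 2 schedules S/F on every study day from D-2 to D7 for both cohorts. No arterial line is needed for it.

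P/F is treated differently. Section 7.2 plans a similar comparison for a subset, "For the ALI group with an arterial line in place", and gives its purpose: "to identify whether any improvement in S/F ratio is due to clinical improvement of ALI". Under Blood Sampling, section 3.1 says "Arterial blood gas samples will only be obtained for patients with an indwelling arterial line" and also "Placement of an Aline is not a requirement for the study". Section 4.1 provides for ALI patients with no gas result ("In the event of inability to obtain arterial blood gas analysis to calculate a P/F ratio") by substituting oxygen-flow criteria. Table 2 lists P/F daily for the ALI cohort, but the sampling rule limits it in practice to patients who have a line.

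Section 7.2 describes the expected drug effect as a higher S/F at a given P/F. It accepts that ALI could improve during dosing, though slowly, and expects no improvement in the ESLD cohort. It gives no rule for P/F after a line is removed, no S/F analysis restricted to patients or days with P/F, no joint analysis of the two ratios, no separate S/F result by cohort and no missing-data method.

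**The concern.** The study is single-arm and open-label, so no control group absorbs spontaneous recovery. Section 7.2 gives the P/F comparison the task of telling recovery from drug effect in ALI. That comparison is informative only if the P/F change and the S/F change describe the same patients at the same times. As written, P/F comes from ALI patients on days with a line, and S/F from everyone in the analysis population. A difference between the two changes can therefore arise from who is in each set, with no drug effect at all.

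The trial exists to supply an effect size for a later study (section 7.1), so a wrong attribution would carry forward into that design.

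**Working it through.** The plan states no figure for this check. It gives N = 20 but no ALI/ESLD split, effect size, SD, alpha, line-removal rate or recovery size. Every numerical input below other than N is therefore an assumption, and the true drug effect is set to zero throughout.

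**1. Mean P/F change when removal is related to recovery.** Let true recovery on the log scale have mean 0.15 and SD 0.20, the same for S/F and P/F. Then exp(0.15) − 1 = 16.2%. Let q be the share of lines out and ρ the correlation between recovery and removal. Among patients who still have a line, the mean log P/F change is

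0.15 − ρ × 0.20 × φ(z)/(1 − q), where z is the standard normal point with 1 − q below it.

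| q | ρ | mean log P/F change | as % | gap to S/F in ALI (16.2%) |
|---|---|---|---|---|
| any | 0 | 0.150 | 16.2 | 0 |
| 0.1 | 0.2 | 0.142 | 15.3 | about 1 |
| 0.3 | 0.5 | 0.100 | 10.6 | about 6 |
| 0.4 | 0.5 | 0.086 | 8.9 | about 7 |
| 0.3 | 1.0 | 0.051 | 5.2 | about 11 |
| 0.4 | 1.0 | 0.021 | 2.1 | about 14 |

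**2. The same P/F values against S/F pooled over both cohorts**, with ESLD change set to zero:

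- 50% ALI: pooled S/F is exp(0.075) − 1 = 7.8%. For q of 0.3 to 0.4 and ρ of 0.5 to 1.0 the gap runs from 7.8 − 2.1 = +5.7 to 7.8 − 10.6 = −2.8 points.
- 25% ALI: pooled S/F is exp(0.0375) − 1 = 3.8%. The gap runs from 3.8 − 2.1 = +1.7 to 3.8 − 10.6 = −6.8 points.
- Removal unrelated to recovery, 50% ALI: 7.8 − 16.2 = −8.4 points. Mixing the cohorts distorts the comparison even without informative removal.

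**3. A second model as a cross-check.** Suppose a share r of ALI patients gain G = 60 ratio units and the rest gain nothing. Lines are out in a share q_r of recovering patients and q_n = 0.1 of the others. Expected P/F change in patients with a line is G·r(1 − q_r) / [r(1 − q_r) + (1 − r)(1 − q_n)], against G·r for S/F in all ALI patients. With r = 0.5, S/F change is 30.0. P/F change is 30.0 at q_r = 0.1, 15/0.70 = 21.4 at q_r = 0.5, and 6/0.55 = 10.9 at q_r = 0.8.

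**4. Effect on the tests.** This model was simulated with SD 25, two-sided 0.05, 20 patients of whom 10 to 20 have ALI, r of 0.3 to 0.5, and 3,000 runs per setting. The share of trials with S/F significant in all patients but P/F not significant in those with a line was:

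- 0.10 to 0.21 when 10% of lines are out regardless of recovery;
- 0.15 to 0.42 when 50% are out regardless of recovery (no bias in the mean P/F change, only lost power);
- 0.14 to 0.77 when 80% of recovering and 10% of other patients have the line out.

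With five patients the smallest two-sided signed-rank p is 2/2^5 = 0.0625, so with five or fewer P/F could never reach 0.05.

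**5. After matching.** With both ratios taken in the same patients at the same times, the expected changes agree (10.9 and 10.9 at r = 0.5, q_r = 0.8). The discordant result falls from 0.32 to 0.03 with 10 ALI patients, 0.58 to 0.06 with 15, and 0.77 to 0.08 with 20. Part of that fall is lower power in the smaller set.

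**The case against.** A reader might infer that the plan prescribes P/F change in remaining line-holders against S/F change in everyone. It does not say so. Its idea of S/F improving at a given P/F points toward a paired comparison, and having a line in place could mean at baseline. But no paired analysis is specified, and the sampling rule ends P/F when the line is out whichever reading is taken.

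A reader might also infer that the check always fails in the drug's favour. The documents do not support this. They do not say that lines are removed on improvement, and step 2 shows the sign can reverse once ESLD patients are pooled. The frequent-but-unrelated case in step 4 also shows that part of the problem is small numbers rather than informative missingness.

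Nor is P/F the only protection in the design. There are 48 hours of stable requirement before dosing, an ESLD cohort not expected to improve, daily P50, and two washout days of S/F that enter the longitudinal model. These help, but section 7.2 gives P50 no analysis role and plans no separate ESLD result.

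Patients whose lines come out need not drop out of P/F entirely. If the similar comparison includes the mixed model, their earlier values stay in. A signed-rank test on a day without a line still loses them.

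Finally, the plan calls ALI progress slow, and no decision rule turns an S/F–P/F gap into an efficacy claim. The first point makes Day 2 less exposed than Day 5. The second limits the consequence to interpretation and the planning of the next study.

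**Conclusion.** The concern holds as a mismatch of analysis sets. P/F and S/F changes come from different patients and days, and section 7.2 does not align them, so their comparison cannot separate ALI recovery from drug effect. ALI patients who never have a line fall into the same gap.

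The direction and size of any bias are not fixed by the documents. Against S/F in ALI patients, with zero drug effect and 16% recovery assumed, the false gap is 0 to about 14 points depending on how many lines are out and how closely removal follows recovery. Against pooled S/F it can be smaller or negative. These figures assume equal log change in the two ratios, and they concern Day 5 more than the Day 2 primary. The change is worth making because it is cheap and matches the plan's own concept.

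**What to change.** In section 7.2:

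- State that the recovery check uses only ALI patient-days with both S/F and P/F. Analyse it as the within-patient difference in log change from baseline, by signed rank at Day 2 and Day 5, or with a mixed model of S/F conditional on P/F.
- Report S/F separately for ALI and ESLD.
- Report by day the number of ALI patients with a line, with the date of and reason for each removal.
- Describe S/F change without paired P/F in ALI patients as not separable from recovery.

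A sensitivity analysis that scores line removal as the largest observed P/F gain should be left out or labelled as a bound. If better saturation on drug prompts removal, it would count drug effect as recovery.

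The cost is SAP wording, one added CRF field for line removal, and fewer patients in the Day 5 comparison.

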# 3 Study Design

## 3.1 General Design

Following a screening period and observation that clinical status is stable and requiring substantial oxygen support for 48 hours, subjects with decompensation of ESLD or ALI with hypoxemia, will be approached for informed consent. The nature of the risks and benefits associated with participation in the study will be explained to all potential study subjects or legally authorized representative (LAR). Written informed consent must be obtained before the subject can begin any screening procedures that are not considered standard patient care.

**Physiological data:** Physiological data at screening, baseline, study day 1-5, and up to two days post voxelotor administration will be recorded from standard of care with the only exception being SpO2/FiO2 (S/F) ratio measurements, which will be obtained at the same intervals but by the qualified and delegated study staff or medical team through the use of an FiO2 weaning maneuver.

Physiological measures to be recorded are detailed on the Schedule of Activities table 2.

**FiO2** Weaning Maneuver: The process of titrating FiO2 down slowly until the study patient's SpO2 measurement is approximately 88%. This will provide the study team with values for an S/F ratio that more closely represents the transition to the steepest part of the oxygen dissociation curve (ODC). Measurements that represent this transition on the ODC will allow for more precise comparison and provide more accurate trending data. Once completed, the oxygen delivery system will be titrated back to achieve SpO2 goals prescribed by the medical team.

**Modified Borg Dyspnea Scale:** Study subjects will be asked to rate their dyspnea symptoms daily to record their perceived shortness of breath.

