#### 7 \* Statistical Plan

# 7.1 Sample Size Determination

This is a pilot study and will be used to determine effect size for future prospective study

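### A flat P/F ratio cannot exclude lung recovery: FiO2 and timing of the arterial gas are unspecified, and the drug's left shift may itself lower P/F

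*Combined protocol and SAP*

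**What the plan says.** Section 7.2 (Statistical Methods) defines the primary and secondary outcomes as change in S/F from baseline to day 2 and to day 5: "Each will be compared using the Wilcoxon Signed Rank test". It accepts that lung recovery is a rival explanation, "as ALI could improve during the 5 day dosing period", and meets it with one extra analysis. In ALI patients with an arterial line, the P/F "ratio will also be compared in a similar manner to identify whether any improvement in S/F ratio is due to clinical improvement of ALI". The reasoning given is that voxelotor should improve the S/F "ratio (the result of left-shift in p50) for a given P/F ratio (the result of pulmonary function limiting PaO" (the quotation stops at the subscript of PaO2). P/F is thus assigned to the lung and p50 to the drug.

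Section 3.1 (General Design) says that physiological data "will be recorded from standard of care with the only exception being" the S/F ratio. S/F is obtained by lowering FiO2 until SpO2 is about 88%, after which oxygen is returned to whatever saturation goal the medical team has set. Arterial gases are taken only where a line is already in place. Neither section 3.1, Table 2 nor sections 6.1 to 6.7 fixes the FiO2 of the gas or its timing relative to the maneuver.

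Section 1.5 states that the drug raises saturation at any given oxygen tension. Table 2 schedules A-a gradient daily in the ALI cohort and P50 daily from the day before dosing. Section 7.2 gives neither a role.

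**The concern.** The study has one arm, so nothing in the design separates drug effect from recovery, and the P/F comparison is the only analysis in section 7.2 assigned to do it. Two features weaken it.

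First, the two ratios are to be interpreted together but, on the natural reading of section 3.1, are not taken under the same conditions. Where there is shunt, P/F depends on FiO2 as well as on the lung.

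Second, P/F need not be independent of the drug. If saturation is higher at a given PaO2, then PaO2 is lower at a given saturation. When FiO2 is titrated to a saturation goal, P/F can fall with unchanged lungs.

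Recovery pushes P/F up and the left shift may push it down, so the two can cancel. The planned logic would then credit the whole S/F gain to voxelotor. Section 7.1 makes that matter beyond this trial: "This is a pilot study and will be used to determine effect size for future prospective study". Recovery counted as drug effect would inflate that figure.

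**Working it through.** The plan gives no figure to reproduce, so this check uses a simple gas-exchange model.

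**From the documents:** S/F read at SpO2 of about 88%; otherwise FiO2 set to a clinical SpO2 goal; the drug shifts the dissociation curve to the left.

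**Assumed (not in the documents):** Hill exponent 2.7; Hb 10 g/dL; a-v O2 difference 4.5 mL/dL; PaCO2 40 mmHg; R 0.8; clinical SpO2 goal 93%; SpO2 equal to SaO2; and the p50 values and lung models below.

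**Formulas**
- Saturation: S(P) = P^2.7 / (P^2.7 + p50^2.7). Inverse: P(S) = p50 × (S/(1−S))^(1/2.7).
- Content: C(P) = 1.34 × Hb × S(P) + 0.003 × P.
- Alveolar PO2: 713 × FiO2 − 40/0.8 = 713 × FiO2 − 50.
- Shunt fraction q: Ca = Cc − q/(1−q) × 4.5, solved for PaO2.

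**1. FiO2 alone (q = 30%, p50 27, no drug).** At FiO2 0.4, alveolar PO2 is 235.2, Cc 14.07 and Ca 14.07 − 1.93 = 12.14. PaO2 is 59.2 and P/F 148. At FiO2 0.6, P/F is 114 (−23%). Over q 25-40% and Hb 10-13 the change is about −19% to −27%. At q = 15% the sign reverses: 241 at 0.4 and 253 at 0.6 (244 and 260 with slightly different constants).

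**2. Left shift alone (q = 30%, FiO2 0.4, p50 27 to 22).** P/F goes from 148 to 122 (−17%), while SaO2 moves only from 89.3% to 89.6%. Over q 25-40% the fall is about 17-18%. At q = 15% and FiO2 0.6 it is about 7%.

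**3. Can recovery be hidden? (q = 30%, p50 26.8 to 21.4, a 20% fall.)** PaO2 at 93% is 69.9 before and 55.8 after; at 88% it is 56.1 and 44.8.

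| Case | FiO2 at 93% | P/F | FiO2 at 88% | S/F |
|---|---|---|---|---|
| Baseline | 0.635 | 110 | 0.332 | 265 |
| Drug only, lung unchanged | 0.614 | 91 | 0.307 | 287 (+22) |
| Drug, and shunt improves to 27.4% | 0.507 | 110 | 0.236 | 373 (+108) |

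The same recovery without the drug gives S/F 333 (+68). P/F is flat, S/F rises by 108, and the drug alone accounts for 22.

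**4. Other lung models (p50 down 20%, P/F at the 93% goal)**
- Fixed A-a gradient of 300, FiO2 = (P(S) + 300 + 50)/713: P/F 119 to 98 with the lung unchanged. A gradient improving to 229 brings P/F back to 119, with S/F 155 to 194 (+39; drug alone +4). At a fixed FiO2, P/F does not change in this model.
- Lognormal V/Q spread: P/F 263 to 228. In its flat-P/F case S/F rises from 428 to 524 (+96; drug alone +41).
- PaO2 proportional to FiO2: no change in P/F, by construction.

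**5. Does matching FiO2 suffice?** No. In the shunt model, P/F at the weaned FiO2 is 56.1/0.332 = 169 at baseline and 44.8/0.307 = 146 on drug with the lung unchanged.

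**6. A-a gradient.** In case 3 at the 93% goal it is 713 × 0.635 − 50 − 69.9 = 333 at baseline, 332 with drug only and 256 with hidden recovery. It separates the two here, but it also depends on FiO2: the same baseline lung at the weaned FiO2 gives 713 × 0.332 − 50 − 56.1, about 130.

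**The case against.** The strongest reply is that every size above is assumed. The text gives no p50 shift in mmHg, no SpO2 goal and no shunt fraction. A reader might infer that the drug necessarily lowers P/F. That is not supported: one of four lung models shows no fall, another shows none at fixed FiO2, and milder disease, which section 4.1 admits, shows a smaller one. Nor can FiO2 de-escalation be said to raise P/F in general, since the direction reverses at 15% shunt.

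A reader might also take the FiO2 mismatch as something the protocol states. It does not. It is the natural reading of section 3.1, where S/F is the sole exception to routine-care data, but S/F is taken at the same intervals, and arterial gases appear among blood samples drawn for the study. What can be said is that the FiO2 and timing of the gas are unspecified.

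On scope, P/F is a supporting comparison in the arterial-line ALI subset of a 20-patient pilot. The primary S/F calculation does not use it. Section 7.2 expects recovery to be slow and none in end-stage lung disease. A clear P/F rise would generally still point to recovery, unless a change in FiO2 explains it.

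These limits stand and reduce the certainty and the scope. They do not rescue the inference from a flat P/F to no recovery. In the shunt model an improvement of 2.6 percentage points (30% to 27.4%) is enough to hide.

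**Conclusion.** The point holds in limited form. As planned, a flat P/F in the ALI subset does not exclude lung recovery, and an S/F gain beside it could be wrongly attributed to voxelotor. The direction follows from sections 1.5, 3.1 and 7.2 read together. The size does not: about a 17% fall in P/F for a p50 shift of 27 to 22 mmHg at 25-40% shunt, about 7% at 15% shunt and FiO2 0.6, and zero if PaO2 is proportional to FiO2, all under the assumptions listed.

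It would go too far to infer that the primary outcome is invalid or that misattribution will occur. The plan permits it and, as written, would not detect it.

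**What to change.** 1. **Section 3.1:** draw the existing arterial-line sample at the end of the weaning maneuver and record its FiO2, so that PaO2, SaO2, SpO2 and FiO2 are simultaneous.
2. **Section 7.2:** state that a flat or non-significant P/F change will not be read as absence of lung improvement.
3. **Section 7.2:** report the A-a gradient and same-day P50 descriptively beside P/F, with the FiO2 of each gas, because the A-a gradient also varies with FiO2.

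Do not use a regression of S/F on same-time P/F and P50 as the test of drug effect. With SpO2 held near 88%, S/F = P/F × 88/PaO2, and PaO2 at 88% is about 2.09 × P50, so the model largely refits the dissociation curve. At a given P/F it would credit the drug with 26.8/21.4 − 1 = 25%, when the drug-only rise in case 3 is 22/265 = 8%. It also adjusts for a P/F that the drug may have lowered.

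The cost is a few sentences and coordinating the draw with the maneuver. No new line or laboratory test is needed, and A-a gradient and P50 are already scheduled.
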